## Project Protocol

### Experimental design

The study consists of a mechanistic randomized placebo-controlled clinical trial with a mixed experimental design, whose objective is to assess which variables that have been linked to central sensitization (CS) in chronic pain patients can predict the response of chronic low back pain (CLBP) patients to spinal manipulative therapy (SMT). In order to do this, clinical, psychophysical and inflammatory variables will be measured in CLBP patients, which will be exposed to either SMT or a placebo SMT for 12 visits over a 4-week period. Another group made up of healthy volunteers will be used to determine the reference values of the same variables in a healthy population and compare them with the clinical population, before and after exposure. The primary outcome measures and main clinical variables are pain intensity and disability. All variables will be measured before the first SMT session, as well as at the end of the twelfth and last session, except for pain intensity, which will be measured at the start of each session for exploratory reasons.

**Figure 1.** Study protocol for the clinical trial

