### **Sample size calculation**

To determine the ideal number of participants, we have considered our first aim, which is to identify the variables linked to the CS phenotype that could help predict the response to treatment based on SMT for CLBP. In order to do this, we will perform a multiple regression analysis, using five independent variables as predictors, in particular the score on the pain catastrophizing scale (PCS) and central sensitization inventory (CSI) questionnaires (indicators of catastrophism and CS), the pressure pain thresholds (PPTs) in the primary pain area (marker of primary hyperalgesia), the urinary levels of the cytokine Tumor Necrosis Factor Alpha (TNF- $\alpha$ ; marker of inflammation) and finally the expectations of relief for each patient (indicative of potential placebo effects). The baseline values of these variables will be included in the multiple regression model. For each predictor variable, it is recommended to estimate about ten sample elements, therefore we predict that a sample size of 50 patients per group will be necessary (Ortega Calvo and Cayuela Dominguez, 2002). Taking into account two groups, one that will receive real SMT and the other placebo SMT, we will need a sample of 100 patients. An additional group of age and sex-matched healthy individuals without CLBP of the same size (50 participants) will be recruited to be used as a reference group, to determine

reference values in a healthy population for the predictor variables (questionnaires, PPTs, cytokines only)

Regarding the two main outcome variables (pain intensity and disability related to low back pain), we expect a reduction in pain and disability after one month in patients who receive 12 sessions of SMT compared to placebo. We aim to detect small to moderate effects since it is a one-month intervention in patients with chronic pain unresolved by other treatments over at least 3 months. Therefore, based on an effect size of  $f = 0.175$ , an alpha of 0.05, a power of 0.8 for 2 groups and 2 repeated measures (baseline and session 12), and a correlation between the repeated measures of 0.5, the size of the necessary sample is 34 patients per group and a total of 68 patients to detect statistically significant changes in clinical pain and disability. Therefore, our analysis based on the regression model to predict the clinical course provides us with a large enough size for both the first and second aims of this study.

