#### *Questionnaires variables*

The PCS and central CSI questionnaires will be completed before the beginning and upon completion of the study (Cuesta-Vargas et al., 2016; Garcia Campayo et al., 2008). Both these variables will be introduced as predictors in the regression model, due to their intrinsic association with a CS phenotype. The PCS will be used to identify specific pain cognitions that are usually present in patients with a CS phenotype, this measure will be used to evaluate the association of CLBP with psychosocial factors described by Smart et al. (Smart, et al., 2012). The CSI is an excellent tool to identify patients compatible with CS mechanisms, particularly when using the cut-off value of 40/100 (Scerbo et al., 2018). Pre and post reference values of these questionnaires will be taken from the healthy population sample in the same time-frame.

In addition, the Beck Depression Inventory II (BDI-II) and the Generalized Anxiety Disorder scale (GAD) questionnaires will be used to screen and quantify symptoms of depression and anxiety (García-Campayo et al., 2010; Sanz et al., 2005). The scores in these questionnaires will be measured both at baseline and follow-up for exploratory purposes and to determine whether significant correlations exist between any of these variables and the primary outcomes of pain and disability.

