#### *Expectations and effectiveness of the blinding*

Before initiating treatment, each participant will be asked about their expectations of pain relief upon completion of the study. To do this, they will give a verbal evaluation using an analog scale with the descriptors -100, equivalent to "total pain relief," 0, equivalent to "no change," up to +100, equivalent to "maximum pain increase". Expectations of pain relief will be used as the fifth predictor in the regression model, allowing to identify the contribution of patients' expectations, which as an important part of the placebo effect and may predict the response to treatment for chronic pain (Cormier et al., 2016).

In addition, in order to confirm the efficacy of the placebo intervention, the participants will respond before the second, seventh and last (twelfth) sessions to the following question: “Do you think that the treatment you have received is a real chiropractic treatment for back pain?”. A second question will ask patients about the degree of certainty with respect to the previous question on a numerical rating scale of 0–10, with 0 being total uncertainty and 10 being absolute certainty (Chaibi et al., 2015). These questions will be answered in an online questionnaire without the presence or interference of any investigators. Potential differences to these questions between the two groups will be examined.

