Official Title:

Efficacy of Chiropractic Spinal Manipulative Therapy in Patients With
Primary Chronic Low Back Pain: a Mechanistic Randomized Controlled
Trial

NCT number: Not Available

Unique Protocol ID: SMTCLBP

Date: December 15th, 2021

Statistical analyses

The normal distribution of the data will be verified using the Kolmogorov-Smirnov test. Data deviating from normality will be transformed to obtain a normal distribution before being entered into the data analysis. The two main outcome variables (clinical pain intensity and disability related to low back pain) will be compared between groups (SMT vs. placebo) over time (baseline and session 12) using a mixed analysis of variance. Average pain intensity since the previous treatment visit and in the seven days prior to the initial visit will be the variable used for statistical analyses. With an exploratory objective, the secondary variables (PCS, CSI, BDI-II, GAD scores, PPTs, degree of pain widespreadness, urinary cytokine levels, number and severity of reported adverse effects, presence of leg pain, pain medication use) will be compared between groups (SMT vs placebo) over time (baseline and session 12) using another mixed analysis of variance. To test a priori hypotheses, significant effects will be decomposed using planned comparisons. For the rest of the effects, Tukey's HSD will be used for testing any pair-wise comparisons between group means.

Pearson's product-moment correlation analyses will be carried out to examine the association between primary variables and secondary variables that demonstrate significant effects between groups over time. Subsequently, two multiple regression models will be used to examine the predictors of improvement in clinical pain and disability over time in patients who have received SMT, using secondary variables with a significant association with the primary variables. The secondary variables used for this analysis will be: baseline PCS and CSI score, baseline PPTs in the primary pain region, baseline TNF- α levels, and baseline expectations of pain relief. In addition, in another

regression model, the changes (delta) in these variables (except expectations of pain relief, since it is only measured at baseline) throughout the 4 weeks of treatment will be used as predictor variables. This is done to identify the variables most associated with clinical evolution, in order to answer the mechanistic question.

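### The baseline-predictor regressions use SMT patients only, so they cannot separate prediction of response to SMT from general prognosis

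*SAP*

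**What the plan says.** The Protocol (Experimental design) describes a placebo-controlled trial whose objective is to find which variables linked to central sensitization predict patients' response to SMT. Its Sample size calculation section calls this the first aim, to identify "the variables linked to the CS phenotype that could help predict the response to treatment based on SMT for CLBP", and sizes the trial on it. The rule is "For each predictor variable, it is recommended to estimate about ten sample elements"; five predictors give 50 per group. The section continues: "Taking into account two groups, one that will receive real SMT and the other placebo SMT, we will need a sample of 100 patients".

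The SAP (Statistical analyses) then plans two multiple regressions for the "predictors of improvement in clinical pain and disability over time in patients who have received SMT". The listed predictors are baseline PCS, CSI, PPT in the primary pain region, TNF-α and expectation of relief. Before this comes a correlation step restricted to "secondary variables that demonstrate significant effects between groups over time". A further regression uses changes in four of the five variables; its population is not stated.

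The placebo arm is used in the mixed ANOVAs, the blinding comparison and the three-group comparison with healthy volunteers. It does not appear in the baseline-predictor regressions.

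**The concern.** In a placebo-controlled trial, a variable predicts response to SMT if the SMT-minus-placebo difference varies with it. That means its slope differs between arms. A slope estimated in the SMT arm alone combines any such difference with natural course, regression to the mean and placebo response, and nothing in that arm can separate them.

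The Protocol itself treats placebo response as a live issue. Expectation is included as a quantity "which as an important part of the placebo effect and may predict the response to treatment for chronic pain". Adjusting for expectation does not remove the other components, and the plan never compares expectation's own slope with its slope under placebo.

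The risk is that a variable which predicts improvement equally well under placebo is reported as a predictor of response to SMT. This touches the aim that sets the sample size, although the randomised data needed to check it are already being collected.

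**Working it through.** **The plan's own figures.** 5 predictors × 10 = 50 per group, 100 patients in total. The separate group-by-time calculation (f = 0.175, alpha 0.05, power 0.8, correlation 0.5) also reproduces: N = 68 gives power 0.812 and N = 66 gives 0.7997. The concern does not depend on either figure.

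**Does any planned analysis compare slopes?**
- The mixed ANOVAs compare mean change between arms and contain no baseline moderator.
- The correlation step selects variables whose own means change differently between arms. That is not effect modification by a baseline value.
- Sizing at 50 per group could hint at a placebo-arm model, but none is written.

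**Screened or fixed predictors.** The SAP can be read as a screened set or as a fixed set of five. Expectation is measured only at baseline, so it cannot show a group-over-time effect, yet it is listed. The fixed reading is used below.

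**Assumptions not in the documents.** 50 per arm, five independent predictors, no dropout, two-sided 0.05; r is the correlation of one predictor with improvement.

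**SMT-only model.** Residual df = 50 − 6 = 44, critical t = 2.015. The noncentrality is about r/√(1−r²) × √44, and power is about Φ(noncentrality − 2.015).
- r = 0.3: 0.3145 × 6.633 = 2.09, power about 0.53
- r = 0.4: 0.4364 × 6.633 = 2.89, power about 0.81
- r = 0.5: 0.5774 × 6.633 = 3.83, power about 0.97

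The formula contains nothing about the placebo arm, so the answer is the same whether the placebo slope equals the SMT slope or is zero.

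**Simulation, 20,000 trials per setting.** The pooled model has 13 parameters: intercept, baseline outcome, arm, five predictors and five interactions (100 − 13 = 87 df).

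| True state | Test | r = 0.3 | 0.4 | 0.5 |
|---|---|---|---|---|
| Same slope in both arms | SMT-only | 54% | 80% | 95% |
| Same slope in both arms | Interaction | about 5% | about 5% | about 5% |
| Slope under SMT only | SMT-only | 53% | 81% | 95% |
| Slope under SMT only | Interaction, unadjusted | 29-30% | 49-52% | 69-76% |
| Slope under SMT only | Interaction, Holm over five | 12-13% | 26-28% | 45-53% |

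Ranges reflect a placebo residual SD of 1 or √(1−r²). As a check on the upper end, the interaction noncentrality is the SMT-only value divided by √2. At r = 0.5 this is 3.83/1.414 = 2.71, and Φ(2.71 − 1.988) = 0.76.

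**Correlated predictors.** PCS and CSI are both entered "due to their intrinsic association with a CS phenotype", so a correlation between them is plausible, though no value is given. If two predictors correlate at 0.5, the SMT-only rates for the purely prognostic variable are 43/69/89% and the interaction rate stays at 5%.

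**Separate check on another scale.** With unit residual SD and a slope of 0.5 (r = 0.5/√1.25 = 0.45), the SMT-only model is significant in 89.0% of trials when placebo has the same slope and in 89.1% when the placebo slope is zero. The interaction test gives 5.2% and 64.0%.

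**The case against.** The strongest reply is that the model is meant to be prognostic. The end of the Protocol's sample size section speaks of predicting the clinical course, the SAP speaks of improvement over time, and neither states a hypothesis of effect modification. On that reading a one-arm model is valid and one sentence limiting the claim would be enough. This part stands: the SMT-only slopes are legitimate prognostic results. But both statements of the aim refer to response to SMT, and without a label readers of a placebo-controlled trial will take the slopes as specific to SMT.

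Second, interactions are weakly estimated with 100 patients. That is true. The smallest slope difference detectable with 80% power is about 0.57 residual SD per predictor SD, against 0.41 for a one-arm slope. Detecting 0.41 as a difference would need about 97 per arm. A null interaction would therefore settle little. This argues for estimates with intervals and cautious wording. The one-arm model's higher power is for a different question.

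Third, the near-equality of 54/80/95% and 53/81/95% follows by construction, because the two states generate the same SMT-arm data. That is correct, and it is the point at issue.

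Fourth, if the predictors are screened rather than fixed, these percentages do not apply as stated. The missing arm comparison remains on either reading.

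**Conclusion.** The concern holds. As written, the two baseline-predictor regressions give the same answer for a purely prognostic variable as for a true modifier of the SMT effect, so they cannot deliver the first aim as stated. That conclusion is structural and needs no numerical assumption. Its size does: the 54/80/95% rates rest on the assumed correlations, a fixed set of five predictors, 50 per arm and no dropout. The point should be settled before analysis, because it decides what may be concluded on the aim that set the sample size. The randomised comparison of pain and disability stands as planned.

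**What to change.** For pain and for disability, model the final outcome in all randomised patients on baseline outcome, arm, the five centred baseline predictors and the five arm-by-predictor terms. With baseline in the model, using improvement instead gives the same interaction terms apart from sign.

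- State that the five enter as a fixed set, or define the screen.
- Report interactions with 95% confidence intervals beside the arm-specific slopes.
- Base any claim of SMT-specific prediction on the interactions, with a multiplicity adjustment such as Holm or an explicit exploratory label.
- Describe SMT-only slopes as prognostic.
- For the model of changes, state the population and describe results as associations. Group-by-change terms should not be read as effect modification, because the changes arise after randomisation.

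**Cost.** SAP wording only, with no new data or patients. The price is precision: the 95% interval half-width is about 0.43 SD for an interaction against 0.30 SD for a one-arm slope. Besides the powers tabulated above, unadjusted power at r = 0.3/0.4/0.5 is 23-24/39-41/57-64% if two predictors correlate at 0.5, and 23-25/39-42/58-63% with 40 per arm. The model has 1 + 1 + 5 + 5 = 12 terms, so the Protocol's own rule would imply 120 patients against 100. With no true modifier and no adjustment, 22% of trials show at least one of five interactions at p < 0.05 per outcome. Across both outcomes the figure is 35-40%, depending on their residual correlation (0.7 down to 0); Bonferroni over ten tests brings it to 4-5%.

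### The SAP gives both a significance condition and a fixed list of five for the regression predictors and does not say which governs; the protocol supports only the list

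*SAP*

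**What the plan says.** The relevant text is the second paragraph of the SAP's Statistical analyses section, which has four steps.

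- Pearson correlations are run between the primary variables and "secondary variables that demonstrate significant effects between groups over time".
- Two multiple regressions then look for predictors of improvement in pain and in disability among patients who received SMT, "using secondary variables with a significant association with the primary variables".
- The next sentence reads as a closed list: "The secondary variables used for this analysis will be: baseline PCS and CSI score, baseline PPTs in the primary pain region", followed by baseline TNF-alpha and baseline expectations of relief. That makes five.
- A further model uses, in the SAP's words, "regression model, the changes (delta) in these variables (except expectations of pain relief, since it is only measured at baseline". That leaves four.

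The protocol has no significance condition. Under Sample size calculation, the first aim is "to identify the variables linked to the CS phenotype that could help predict the response to treatment based on SMT for CLBP", by multiple regression "using five independent variables as predictors", and "The baseline values of these variables will be included in the multiple regression model". Its sections on questionnaires, quantitative sensory testing, laboratory tests and expectations then assign each of the five to the model, again without condition.

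**The concern.** Two adjacent SAP sentences give two rules for what enters the model. One makes entry depend on a significance test; the other names the contents. The SAP does not say whether the five all enter, are candidates to be screened, or describe the expected outcome of screening. It gives no alpha for the condition. It also does not say whether the association is tested in the SMT arm or in both arms, or on baseline values or changes.

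This regression serves the first aim and sets the sample size. If the condition were followed, some of the five planned predictors would probably be missing from the fitted model. If the screen and the model used the same patients, the overall test of the model would no longer hold its nominal level.

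**Working it through.** **1. The plan's own figure.** The protocol allows about ten patients per predictor and names five predictors: 10 x 5 = 50 per group, and 2 x 50 = 100 patients. This reproduces the protocol's statement, "therefore we predict that a sample size of 50 patients per group will be necessary". The sample size therefore presupposes that all five enter.

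**2. The two rules side by side.**

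| Source | Rule for entry | Condition |
|---|---|---|
| SAP, regression sentence | secondary variables associated with the primary variables | significant association |
| SAP, next sentence | five named baseline variables | none |
| Protocol, Sample size calculation | the same five baseline values | none |
| Protocol, Questionnaires variables | PCS, CSI | none |
| Protocol, Quantitative sensory testing | PPT at the most painful segment | none |
| Protocol, Laboratory tests | TNF-alpha | none |
| Protocol, Expectations and effectiveness of the blinding | expectations, as fifth predictor | none |

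The condition appears once, in the SAP only.

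**3. What the condition would do if applied.** Assumptions, none of them in the documents: two-sided alpha 0.05; independent predictors; a Pearson test of each baseline value against improvement; the same correlation in both arms when all 100 are screened. The regression is fitted on the 50 SMT patients in every case. Because the SAP does not name the patients for the Pearson test, both screen sizes are shown.

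The smallest correlation that passes is r = t / sqrt(n - 2 + t²), with t the 97.5% point on n - 2 degrees of freedom. This gives 0.279 at n = 50 and 0.197 at n = 100.

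*Five true predictors, each correlated 0.3 with improvement* (total R-squared 5 x 0.3² = 0.45; 10,000 simulated trials):

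| | Screen on 50 | Screen on 100 |
|---|---|---|
| One given predictor passes | 0.57 | 0.86 |
| Mean number entering | 2.9 | 4.3 |
| All five enter | 5% | 47% |

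As a rough check, 0.57⁵ = 0.06 and 0.86⁵ = 0.47. At a correlation of 0.2 (total R-squared 5 x 0.2² = 0.20), all five enter in 0.1% and 3% of trials.

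*Five null predictors* (20,000 simulated trials; a trial admitting none counts as not rejecting):

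| | Screen on 50 | Screen on 100 | Fixed five |
|---|---|---|---|
| At least one admitted | 22% | 23% | not applicable |
| Overall F test rejects | 22% | 8% | 5% |
| Any significant coefficient | 22% | 8% | 21% |

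The first row agrees with 1 - 0.95⁵ = 0.226.

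**The case against.** The strongest reply is that the documents largely settle the matter. The list comes straight after the condition and is specific, the protocol commits each of the five, and 50 per group is built on five. A predictor dropped by screening would be a visible departure from the protocol. This stands, and it makes the fixed list the likelier intent. It does not remove the condition, which remains in the SAP as a stated rule.

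A reader might infer more than the documents support in two ways.

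- *A two-stage filter.* Because the regressions are described as following the correlations, the group-over-time requirement might be taken as a first entry step for the regression. The text attaches that requirement only to which variables are correlated. Expectations are measured at baseline only and could never meet it, yet they are on the list of five. The list itself speaks against this reading, so no figures are given for it.
- *More false-positive predictors.* Screening does make an admitted null predictor likely to look significant (93% of those admitted by a screen on the 50, 32% on all 100). That is conditional on admission. The chance that a null trial shows any significant coefficient does not rise. What remains is the overall F test and the loss of planned predictors.

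Independence is also doubtful, for instance between PCS and CSI. With a correlation of 0.3 among null predictors and a screen on 50, the F test still rejects in 21% of 4,000 simulated trials, against 4.5% for the fixed five. The drop-out figures are more sensitive. With standardised predictors, coefficients of 0.3, 0.2, 0.2, 0.1 and 0.1 and residual SD 1, all five pass in 22% of trials at that correlation, against essentially none when the predictors are independent.

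**Conclusion.** The point holds as a conflict within the SAP and between the SAP and the protocol, and it should be fixed. Confidence is high on the text. The consequence depends on which rule is followed. On the fixed-list reading nothing changes. Under the condition, screening on the SMT arm would usually remove planned predictors and raise the null rejection rate of the overall F test about fourfold (22% / 5% = 4.4). Screening on all 100 patients does less harm (8% against 5%). These sizes rest on the assumed alpha, correlations and form of the Pearson test, and they illustrate the risk rather than forecast it. The protocol's 50 per group is not in question.

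**What to change.** In the SAP, delete the significance condition as an entry rule. State that all five named baseline predictors enter both the pain and the disability models, and that all four changes enter the delta model, whatever the analysis-of-variance or correlation results. Label the Pearson correlations descriptive.

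The cost is two or three sentences, with no added data or patients: five predictors in 50 SMT patients is what the protocol's sample size already assumes.

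### The regression on change scores omits baseline expectation of relief for a reason that does not require it, leaving a possible confounder unadjusted in the model meant to address mechanism

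*SAP*

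**What the plan says.** The SAP (Statistical analyses) first describes two regressions of "the predictors of improvement in clinical pain and disability over time in patients who have received SMT". Their candidate predictors are five baseline measures: PCS, CSI, pressure pain threshold in the primary pain area, urinary TNF-α and expectation of relief.

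It then adds another regression in which the changes in these variables "throughout the 4 weeks of treatment will be used as predictor variables". Expectation is left out of that model, with one reason given: "except expectations of pain relief, since it is only measured at baseline". The stated purpose follows directly: "This is done to identify the variables most associated with clinical evolution, in order to answer the mechanistic question".

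The protocol gives expectation a specific job. In Sample size calculation it is one of the five predictors and is described as a sign of possible placebo effects. In Expectations and effectiveness of the blinding the plan is that "Expectations of pain relief will be used as the fifth predictor in the regression model"; the same sentence calls expectation an important part of the placebo effect and says it "may predict the response to treatment for chronic pain".

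Neither document brings expectation back into the change-score model as a baseline covariate, or plans a sensitivity analysis that does.

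**The concern.** Being measured once is a reason for a variable to have no change score. It is not a reason to leave it out of a model of changes, where a baseline covariate needs no change score of its own.

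Pain, disability, PCS and CSI are all self-reported. A patient who expects relief may report improvement on all of them together. If so, a fall in PCS or CSI would track a fall in pain even with no direct link between them. The regressions are described for patients who received SMT, so the randomised comparison with placebo does not protect these associations.

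At stake is how the mechanistic result is read. An association between falling catastrophising and falling pain could be reported as a clue to mechanism when both follow an expectation that the trial has already measured. The randomised comparison of pain and disability is not affected.

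**Working it through.** **The plan's own figure.** The protocol sizes the regression by this rule: "For each predictor variable, it is recommended to estimate about ten sample elements". With five predictors, 5 × 10 = 50 per group, which reproduces the stated size. The change-score model has four terms (4 × 10 = 40). With baseline expectation it has five (5 × 10 = 50), which equals the planned SMT arm.

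**Inputs for the bias.** From the documents: n = 50 in the SMT arm and four change scores. Assumed, because the documents give no values: r, the correlation of expectation with a change score, and g, its correlation with improvement in pain. All variables are standardised, the direct effect of each change score on pain is zero, and tests are two-sided at 5%.

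**Size of the spurious slope.** If one change score shares expectation with the outcome, the slope without expectation is

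0 + g × r.

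If PCS change and CSI change both do, with one common correlation r for PCS change, CSI change and pain change, those two changes correlate r² with each other and r² with pain change. Solving the two normal equations gives each a slope of

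r² / (1 + r²).

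- r = 0.2: 0.04/1.04 = 0.038
- r = 0.3: 0.09/1.09 = 0.083
- r = 0.4: 0.16/1.16 = 0.138
- r = 0.5: 0.25/1.25 = 0.200

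With expectation in the model the expected slope is zero throughout.

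**False-flag rates** in the equal-correlation setting, by simulation with at least 6,000 trials per setting (ranges reflect simulation error):

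| Common correlation | PCS flagged, expectation omitted | PCS flagged, expectation included | PCS or CSI flagged, omitted | PCS or CSI flagged, included |
|---|---|---|---|---|
| 0.2 | about 6% | about 5% | 10–11% | about 10% |
| 0.3 | 8–9% | about 5% | about 16% | about 10% |
| 0.4 | about 15% | about 5% | about 28% | about 10% |
| 0.5 | 27–28% | about 5% | about 50% | about 10% |

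At 0.1, PCS change is flagged in about 5% of trials. The benchmark for the last two columns is 10%, not 5%, because two tests are made: 1 − 0.95² = 0.0975.

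If only one change score is related to expectation, the rate is about 9.5% at r = g = 0.3 and about 40% at r = g = 0.5. At r = 0 there is no bias.

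**Cost of adding the term.** Residual degrees of freedom go from 50 − 5 = 45 to 50 − 6 = 44, and the critical t from 2.014 to 2.015. That is the whole cost only if expectation is unrelated to the change scores. If it correlates r with PCS change and acts on pain only through PCS change, adjustment also inflates the standard error of the PCS slope by about 1/√(1 − r²): 1.048, 1.091 and 1.155 at r = 0.3, 0.4 and 0.5. Simulated power for a true partial correlation of 0.4, n = 50:

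| r | Expectation omitted | Expectation included | Loss (points) |
|---|---|---|---|
| 0 | 80–81% | about 80% | about 1 |
| 0.3 | 80–81% | 76–77% | about 4 |
| 0.4 | 80–81% | 73–74% | about 7 |
| 0.5 | about 80% | 68–69% | 10–12 |

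**The case against.** The strongest case for the omission has four parts.

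1. **The confounding path is not in the documents.** They say expectation may predict outcome. Nothing says it moves PCS or CSI. At correlations of 0.2 or below, the false-flag rate is close to nominal. This stands: the claim has to be of a possible confounder.

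2. **Expectation may be upstream of the mechanism.** If it works by lowering catastrophising, the unadjusted PCS slope is not biased and adjustment only costs precision, as the power table shows. The SAP's stated aim is also one of association. This stands too, and is why one fixed adjusted model should not simply replace the unadjusted one. But the SAP does not argue for omission on this ground, and a reader could not tell the two structures apart from the unadjusted model alone.

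3. **The baseline models already examine expectation.** A reader will see there whether it predicts improvement, and a weak association would suggest little bias. That is useful, but it does not adjust the coefficients in the change-score model. The SAP also speaks of using variables with a significant association with the primary outcomes, so even its place in the baseline models could be read as conditional.

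4. **There is no spare sample size.** Five terms meet the ten-per-predictor rule only if all 50 SMT patients complete, whereas four terms tolerate ten losses. True, but the planned five-predictor baseline model has the same limit.

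**Conclusion.** The point holds in a limited form. The stated reason does not justify dropping expectation, and the protocol's own account of expectation as a placebo marker argues for having it in the model that is to inform mechanism. As written, that model leaves a possible confounder unadjusted although it has been measured.

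The size depends wholly on correlations that the documents do not give. The consequence runs from nothing at zero correlation, through near-nominal at 0.1–0.2, to a false flag for PCS change in about 15% of trials at 0.4 and 27–28% at 0.5, against about 5% with adjustment. The check also assumes that the change-score model uses the same arm and outcomes as the sentences before it, which the SAP does not restate, and that all 50 patients contribute.

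Two stronger readings are tempting. A reader might infer that expectation is an established common cause, so that any PCS or CSI finding would be spurious. The documents support only the link from expectation to outcome. A reader might also infer that adjustment would settle the mechanistic question. It would not: the model stays observational, and other shared causes remain.

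**What to change.** In the SAP (Statistical analyses), replace the exclusion with a statement that the change-score models include baseline expectation of relief as a covariate beside the four change scores, and that each model is reported with and without it. If the PCS or CSI coefficient shrinks on adjustment, the report should say that the data cannot separate confounding by expectation from an effect of expectation that passes through those variables.

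State in the same place that these models use the SMT arm and improvement in pain and disability, if that is what is meant.

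The cost is SAP wording and one degree of freedom, with no new data, visits or patients. The power loss in the adjusted model is about 1 point if expectation is unrelated to the change scores and up to 10–12 points in the least favourable setting examined. The model without the term is still reported, so that information is not lost.
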